11.2 Ethics Safety Reporting

Reporting of USADEs to the REC and IRIC

The Sponsor will report all USADEs to the ethics committee within 15 days of the PV office becoming aware of the event, via the 'report of serious adverse event form' for non-CTIMPs published on the Health Research Authority web site.

The form will be completed in typescript and signed by the Chief Investigator. The CI or delegate will submit reports relating to the medical device that meets the above criteria to the Incident Reporting and Investigation Centre (IRIC – part of NHS National Services Scotland).

Annual reports to REC

Annual progress reports will be made on the anniversary of the original REC approval.

Once the study has ended, we will declare the end of study to the Research Ethics committee (REC) that gave a favourable opinion within 90 days of the study ending using the appropriate method. This will be followed up with the final report within 12 months of the end of the study.

11.3 Study Management

11.3.1 Trial Steering Committee

No Trial Steering Committee is required for this study.

11.3.2 Trial Management Group

A Trial Management Group (TMG) will convene consisting of the representatives from the Sponsor (GSTT) including the CI, co-investigators, statisticians, PPI leads and the Study Manager (including project managers from each participating Trust). The role of the group is to monitor all aspects of the conduct and progress of the trial, ensure that the protocol is adhered to and take appropriate action to safeguard participants and the quality of the trial itself.

11.3.3 Data Monitoring Committee

No Data Monitoring Committee is required for this study.

11.4 Ethics & Regulatory Approvals

Prior to commencing the study, approval will be sought from an appropriate REC. The research will be undertaken in accordance with the principles of Good Clinical Practice and the Declaration of Helsinki. The CI will be responsible for updating the Ethics committee of any new information related to the study.

11.5 Protocol Amendments

Any change in the study protocol will require an amendment. Any proposed protocol amendments will be initiated by the CI following discussion with the sponsor and any required amendment forms will be submitted to the ethics committee and sponsor.

The CI will liaise with study sponsor to determine whether an amendment is non-substantial or substantial. All amended versions of the protocol will be signed by the CI and Sponsor representative.

Before the amended protocol can be implemented favourable opinion/approval must be sought from the original reviewing research ethics committee (REC) and Research and Development (R&D) office.

12 COMPLIANCE AND WITHDRAWAL

12.1 Participant compliance

Not applicable for this study as data is collected only from the existing data records. Specific study participant interviews are not required for the study data collection and there will be no change in standard of care.

12.2 Withdrawal / dropout of participants

If patient has selected National Data opt-out, their data will be excluded from final analysis. Patients who wish to withdraw their data from being used in this research will be removed from analysis prior to anonymisation. Data extracted will be destroyed and the patient withdrawn from this part of the study if requested. The contact information for the research team will be made available to patients through posters and other publications within the department to allow them to express their wish to withdraw their data from the research.

12.3 Protocol Compliance

The CI will monitor any protocol deviations and list them in a deviation log /include a file note in the TMF/Site file where applicable. Significant deviations to the protocol or deviations which are found to frequently recur will be assessed by the CI to see if an amendment to the Protocol is required. These will be reported to the sponsor and action taken through Corrective and preventative Actions (CAPA). The CI and sponsor will be notified immediately of a serious breach, where applicable. The Breach will be reported to the REC Committee with the Sponsor in copy within 7 calendar days of the breach being confirmed as serious.

13 DATA

13.1 Data to be collected:

Evaluation sites will periodically collect, clean, link, de-identify and supply data in an agreed format, beginning with baseline data from the pre-implementation phase until the end of the post-implementation phase. The frequency of data collection is subject to change though depending on the feasibility of sites.

A data dictionary will be supplied (example included in the Appendix) that will support fulfilling these requirements from:

Extraction of routinely collected hospital data:

- Referral Data: Age, Sex, date of referral for CT, date of appointment. Where possible ethnicity and deprivation will be captured.
- Radiology Data: Number of referrals, Datetime CT acquired, Datetime CT reported, presence or absence of discordance between qER and reporting radiologist, CT device manufacturer/ type, Usual Care Report
- Clinical Data: Clinical Diagnosis, treatment initiation, referral, including date of death if applicable.
- Follow-up Data: Length of stay ED, Length of stay Hospital, Specialty pathway.
- qER data outputs from qER interpretation
- Changes in treatment pathways after implementation
- Time to diagnosis

Data linkage for follow-up (death within 28 days of Head-NCCT acquisition date) against outcomes will be collected for 28 days.

Data dictionary is attached as a separate document (Appendix 5).

13.2 Data handling and record keeping

Raw medical data from clinical information systems shall be anonymized using native anonymizing export functions that are available using applications. Where a native anonymizing facility is not available to the researcher, other bespoke methods will be provided depending on the datatype (e.g. DICOM images, JSON files etc.).

13.3 Data sharing

The qER algorithm only analyses the NCCT Images and is done on site. GSTFT will act as the central research team. A clinical research fellow will collect anonymized data from the other sites for the final analysis. This data will be shared by other research sites through a secure KCL repository for the duration of the study in a password-protected database on an encrypted hard drive. This data will not be added to a public/private data repository at the end of the study period.

13.4 Information Governance and Security

Each site will have a data processing agreement (DPA) or equivalent with qER to cover the interpretation of NCCT. Each site, with the assistance of qER, GSTT and other internal stakeholders as appropriate, will produce a Data Protection Impact Assessment (DPIA) and a

System Security Policy (SSP), or local alternatives. These will be substantively similar to the templates in Appendix. A site may require further information governance and security documentation (e.g., imaging governance assessments, etc.), depending upon local operating procedures. We will produce a single 'master' DPIA and separate SSP for the project, which can be amended as necessary for each site.

As Qure.ai are compliant with the ISO27001 information security standard and use a commonly accepted approach to processing patient and personal data within a healthcare environment, we expect that sites will accept their information handling and systems approach.

13.5 Personal Data Breaches

Personal data breaches will be immediately reported to the Sponsor/data controllers and to the Data Protection Officer/IG Department of the site that incurred the breach. The following information will be provided to assess the full risk/impact of the breach: full details as to the nature of the breach, an indication as to the volume of material involved, and the sensitivity of the breach (and any timeframes that apply), steps that have been taken to mitigate the risk (trying to retrieve the data asking third parties to delete information that was sent to them in error).

Sites will additionally follow their Trust incident reporting mechanisms and will document this within their TMF/ISFs in the form of a file note provided by the sponsor with corrective and preventative measures addressed.

The sponsor/data controller will determine whether the breach meets the definition of a serious breach and warrants reporting to the regulators including the ICO.

14 MONITORING AND AUDITING

The Chief Investigator will be responsible for the ongoing management of the study. The Sponsor will monitor and conduct audits on a selection of studies in its clinical research portfolio. Monitoring and auditing will be conducted in accordance with the UK Policy Framework for Health and Social Care and in accordance with the Sponsor's monitoring and audit procedures.

15 STATISTICAL CONSIDERATIONS

15.1 Sample Size

The sample size available for analysis is determined by the number of hospitals taking part in the study and the number of patients coming through the Emergency Department requiring a NCCT during the study period.

The proposed study is a stepped-wedge trial, in which all participating sites will receive the intervention, in a random order, throughout the study period. With 4 participating sites, within a 12-month study period, study sites will receive the intervention in a staggered manner (Figure 1). During the study, each site will have received the intervention at a certain time-point. The specific time point for when the site is will be switched from current standard pathway group to intervention group will be allocated based on randomisation procedure.

Baseline data for all sites prior to the start of the study will be available from electronic records. Follow-up data will be available throughout the study period, including at least 3 months post-intervention at all sites. It is likely that changes in treatment pathways after implementation will take time to reach a steady state, and one of the objectives of any analysis will be to model the transition from the pre-intervention to post-intervention state.

This design has elements of a cluster-randomised trial, and of a before-and-after study. Within each site, there will be sufficient statistical power to detect a 20% change in average outcomes (TAT measure) achieved before and after the implementation of the intervention.

The power estimations were conducted via a simulation approach. The range of conditions for sample size and intraclass correlation coefficient (ICC) were tested. The values of sample sizes tested ranged from 120 to 600 abnormal scans per site per year, while the range of ICC ranged from 0.05 to 0.30. Assuming type I statistical error at the $\alpha=0.05$ level and the total duration of the study 12 months the generalized linear mixed-effect regression model (GLMM) with expected distribution of the outcome variable Gamma the total sample size of 1,680 abnormal scans (35 abnormal per site/month; total yearly per site 420) ensures satisfactory level of statistical power exceeding 80% for detecting reduction in TAT by 20%. The models were estimated for abnormal cases. Assuming that abnormal cases are only ~10% of all CT scans performed at sites it can be expected that the total number of available scans in this study will be 16,800. Simulations were performed in R version v.4.1.0. If the study was conducted in a single hospital, this would not provide definitive evidence. However, if a similar impact is observed across four sites, especially if the time course of changes in multiple outcomes track the implementation of the intervention within each site, then the study will provide compelling evidence of the impact of the intervention. Given the expected amount of data that will be generated as part of the study, then it is expected that there will be good power to detect intervention effects within subgroups of patients, defined by age, sex, deprivation, and final diagnosis.

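### Section 15.1 promises good power within subgroups, but its only quantified result, above 80% pooled over 1,680 abnormal scans, does not support that for turnaround time

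*Protocol*

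**What the plan says.** All the power statements stand in Protocol Section 15.1. The simulation used a Gamma mixed model at a type I error of 0.05, and the chosen design is a "total sample size of 1,680 abnormal scans (35 abnormal per site/month; total yearly per site 420"). This, the section says, "ensures satisfactory level of statistical power exceeding 80% for detecting reduction in TAT by 20" per cent. It adds that "The models were estimated for abnormal cases", and obtains 16,800 scans in all by assuming that about 10% are abnormal.

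Two ranges were explored. For scan numbers, "The values of sample sizes tested ranged from 120 to 600 abnormal scans per site per year"; separately, ICC values between 0.05 and 0.30 were tried. No power is reported for any size other than 420 per site-year. The ICC and the Gamma shape behind the reported figure are not stated.

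The same paragraph ends by citing the expected amount of data and concluding that "there will be good power to detect intervention effects within subgroups of patients, defined by age, sex, deprivation, and final diagnosis". It gives no subgroup sizes, subgroup effect or subgroup power.

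Two other sentences in 15.1 bear on the point. One says of pre-study data: "Baseline data for all sites prior to the start of the study will be available from electronic records". The other says: "Within each site, there will be sufficient statistical power to detect a 20% change in average outcomes".

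Section 6.2 restricts the primary outcome to patients with prioritised findings. Section 8.3 says deprivation will be recorded only where that can be done.

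**The concern.** A design sized to give somewhat more than 80% power for one pooled effect normally has much less power for the same effect in part of the data. The large total of 16,800 scans does not help here, because about nine tenths of them are outside the abnormal set on which the TAT power was calculated.

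The stake is interpretation. If TAT shows no significant reduction in, say, one sex, a deprivation group or a diagnosis group, a reader could take that as evidence of no effect because the protocol said power there was good. Sex is the most favourable of the four factors, since it splits the scans roughly in half. Final diagnosis has several categories, and deprivation may be missing for some patients, so those subgroups are likely to be smaller.

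**Working it through.** **Inputs from Section 15.1.** Type I error 0.05; TAT reduction 20%; 35 abnormal scans per site per month; 4 sites; 12 months; pooled power above 80%.

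**Assumptions.** Two-sided test; effect on the log scale, |ln 0.8| = 0.223; same 20% effect in the subgroup; information proportional to the number of scans.

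**1. The plan's own counts.** 35 × 12 = 420 per site; 420 × 4 = 1,680; 1,680 / 0.10 = 16,800. All reproduce. The 80% figure cannot be reproduced uniquely, because the TAT spread and the ICC used are not stated and the step times, shown in Figure 1, were not available for this check. It is plausible: a stepped-wedge generalised least squares model on the log-mean scale, with ICC 0.05 or 0.30 and four assumed step schedules, reaches 80% at a TAT coefficient of variation (CV) of about 0.50 to 0.82.

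**2. Power in a subgroup holding a fraction f of the abnormal scans.**

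Power(f) = Φ( √f × (1.960 + z_pooled) − 1.960 )

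For f = 1/2 and pooled power 80%: 0.7071 × (1.960 + 0.842) − 1.960 = 0.021, and Φ(0.021) = 0.508.

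| Pooled power | Half | Third | Quarter |
|---|---|---|---|
| 80% | 51% | 37% | 29% |
| 90% | 63% | 47% | 37% |
| 95% | 72% | 55% | 44% |

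**3. Pooled power needed for 80% in the subgroup.** Φ(2.802 / √f − 1.960). For a half: Φ(3.962 − 1.960) = Φ(2.002) = 97.7%. For a third: Φ(4.853 − 1.960) = Φ(2.893) = 99.8%.

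**4. Effect detectable with 80% power, if pooled power is 80%.** 1 − exp(−0.223 / √f): about 27% in a half and 36% in a quarter, against the 20% planned for.

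**5. Check of the scaling.** In the model of step 1, with the CV set so that pooled power is 80% and the cell size cut to 35 × f, power is 51–52% in a half, 37–38% in a third and 29–31% in a quarter, across both ICC values and all four schedules. The missing ICC and step times therefore matter little once pooled power is fixed.

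**6. Effect of pre-study records.** Assumptions: CV 0.75, sites switching after months 3, 5, 7 and 9, implementation month dropped, fixed site effects, and 12 extra baseline months at 35 scans per site-month.

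| Calendar time | Half, no baseline | Half, 12 baseline months | Third, 12 baseline months |
|---|---|---|---|
| Categorical months | 51% | 61% | 45% |
| Linear trend | 54% | 91% | 77% |

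This agrees with step 2. Inverting the formula, 61% in a half corresponds to pooled power of Φ((1.960 + 0.279) × 1.414 − 1.960) ≈ 89%, and 91% in a half to Φ((1.960 + 1.341) × 1.414 − 1.960) ≈ 99.7%. Good subgroup power thus needs pooled power far above the stated bound.

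**The case against.** The strongest case for the sentence has five parts.

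- **It is wider than TAT.** It speaks of intervention effects in general and rests on all the data the study will generate. This stands: outcomes analysed in all 16,800 scans are not covered by the calculation, so the sentence should be limited, not struck out for every outcome.
- **The pooled figure is only a lower bound.** This also stands. True pooled power could be high enough, but the protocol does not say so, and even 95% leaves a half-size subgroup at 72%.
- **The simulated range of 120 to 600 per site-year includes 210 and 140, the sizes of a half and a third.** True, but no result is reported below 420, so the range shows neither good nor poor power.
- **Pre-study records add information.** This stands and is the main limit on the figures. With a linear time trend and a full assumed baseline year, a half-size subgroup passes 80%; with categorical months it does not. The amount of baseline data is not stated.
- **No TAT subgroup test by age, sex or deprivation is listed in Sections 6.2, 6.3 or 15.2.** That limits the consequence to how later subgroup results are read. The power statement is still made.

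A reader might also infer that the sentence on sufficient power within each site is wrong. The documents do not support that. Single-site power for an unadjusted before–after test runs from about 26% to 99%, depending on an assumed CV, the switch month and the amount of baseline data. The low end needs a CV of 1 or more. Under the step 6 assumptions without baseline data, the month-adjusted model gives only about 56% pooled power at a CV of 1, which is inconsistent with accepting the protocol's pooled figure. Section 15.2 already places the per-site Wilcoxon tests among exploratory analyses.

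**Conclusion.** The point holds for TAT in abnormal scans: the one power result in Section 15.1 does not support good power within subgroups by age, sex, deprivation or final diagnosis. At pooled power of 80% to 95%, a half-size subgroup has about 51% to 72% and a quarter-size one about 29% to 44%.

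A reader might go further and conclude that subgroup power is shown to be low, or that the study is underpowered overall. Neither follows. The pooled figure is a lower bound and is not disputed, and baseline data could lift subgroup power to an adequate level under favourable assumptions. The figures rest on a two-sided test, the same 20% effect in each subgroup, and information proportional to scan count. Random site-by-month variation would make power fall less steeply with subgroup size, but would also lower the pooled power.

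The sentence should be corrected. It does not affect the sample size or the primary analysis.

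**What to change.** In Section 15.1, limit the subgroup sentence so that it no longer covers TAT in abnormal scans, or replace it for that outcome with power simulated at subgroup size: for example 420 / 2 = 210 abnormal scans per site-year for a half and 420 / 3 = 140 for a third. State the Gamma shape, the ICC, the form of calendar time and any pre-study data used in those runs. Label TAT subgroup analyses exploratory. The within-site sentence and statements about all-scan outcomes need no change on this ground.

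The cost is a wording change, a few further runs of the existing R simulation, and probably a less favourable stated subgroup power. Enrolment and the primary analysis stay as they are.

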15.2 Statistical Analysis Plan

To investigate the reduction in TAT (the outcome variable) the multistage data analysis process will be applied in the study. Initial statistical analyses will consist of basic descriptive analyses, and within-site descriptions of changes in outcomes relating to the patient pathway. As a first step also the graphical inspection of the distributions of variables at each site and time points will be conducted. At this stage the shape of the distribution of outcome variable will be assessed. All outlying observations will be detected and checked. In the next step exploratory univariate analyses will be applied. Since the outcome variable is expected to be continuous and highly right-skewed, we are going to apply non-parametric tests Wilcoxon tests to compare the outcome variables between pre- and post-intervention at each site.

In the second step generalized linear mixed-effect regression model (GLMM) will be applied to the data. The assumed structure of the data will be multilevel with measures nested within sites. The specific model to be applied is going to be GLM rather than normal linear regression model since the distribution of the outcome variable is expected to be Gamma (a non-negative continuous values, right skewed). Within our modelling process we will be controlling for study centre, intervention, calendar month, after-hours reporting, individual patient diagnosis

(ground truth indicating bleed, infarct, presence/ absence of midline-shift, mass-effect, and cranial fracture).

The regression coefficients obtained after the model fit will be investigated to find if there is statistically significant reduction in TAT with qER based reporting and triage. Specifically, the applied models will be used to explore the time course of outcomes within sites, in relation to the timing of the implementation of the intervention, allowing for differences between sites, and over time across all sites. Results will be adjusted for individual patient characteristics.

16 PEER REVIEW

The protocol has been reviewed by all investigators including principal investigators from each site, clinical research science team at Qure.ai (manufacturer of qER), study statistician, members of the PPI group and members of trial management group.

17 FINANCING

This study has been awarded funding from NHSx AI Award. Funding for the study team to deploy and use qER for the study purpose, to perform its analysis of the data gathered from sites, and to produce a final report, is confirmed under the research contract between Qure.ai (manufacturer of qER) and Guys and St Thomas' NHS Foundation Trust. Funding for evaluation sites (those contributing data to the study) is allocated from the AI award to the technology provider (Qure.ai).

Award reference number: AI_Award02354.

18 INSURANCE AND INDEMNITY

This study is sponsored by Guy's and St Thomas' NHS Foundation Trust (GSTFT) and indemnity is provided through NHS Resolution's Clinical Negligence Scheme for Trusts (CNST) which provides indemnity for clinical negligence. In the case of negligent harm, health care professionals undertaking clinical trials or studies on volunteers, whether healthy or patients, during their NHS employment are covered by NHS Resolution. In the case of non-negligent harm, legal liability does not arise where a person is harmed but no one has acted negligently. In exceptional circumstances NHS bodies may consider whether an ex-gratia payment could be offered.

